Appendix 2: Instructions for use of Twisthaler®

HOW TO USE

Before first use, remove the TWISTHALER® from its foil pouch.

Step 1. Open inhaler

Hold the inhaler straight up with the portion (the base) on the bottom (Figure 1). It is important that you remove the cap of the TWISTHALER® while it is in this upright position to make sure that you get the correct dose.

[figure not shown]

Figure 1 – Cap Removal

Holding the base, twist the cap in a counterclockwise direction to remove it. As you lift off the cap, the dose counter on the base will count down by one. (If you began with the dose counter reading "60", this action will cause it to now read "59".) This action loads the device with the dose that you are now ready to inhale.

IT IS IMPORTANT TO NOTE that the indented arrow (located on the portion of the TWISTHALER®, directly above the base) is pointing to the dose counter (Figure 2).

[figure not shown]

Figure 2

Step 2. Inhale dose

Exhale fully. Then bring the TWISTHALER® up to your mouth with the mouthpiece facing toward you. Place it in your mouth, holding it in a horizontal position as illustrated (Figure 3). Firmly closing your lips around the mouthpiece, take in a fast, deep breath. Since it is a very fine powder, you may not be able to feel or taste it after inhalation.

[figure not shown]

Figure 3 – Inhalation

Remove the TWISTHALER® from your mouth and for about 10 seconds or as long as you comfortable can.

IMPORTANT: DO NOT BREATHE OUT THROUGH THE INHALER.

After you use your inhaler, it is important that you wipe the mouthpiece dry, if necessary, and immediately replace the cap firmly closing the TWISTHALER® (Figures 4 and 5).

This is the only way to be sure that your next dose is properly loaded. Be sure that the arrow is in line with the dose-counter window. The cap needs to be put back on and turned in a clockwise direction, as you gently press down. You'll hear a distinctive "click" to let you know that the cap is fully closed.

[figure not shown]

Figure 4 – Closing the Inhaler

Figure 5 – Closed inhaler

IT IS IMPORTANT TO REPEAT STEPS 1 AND 2 EACH TIME YOU INHALE. Rinse your mouth after using.

STORING YOUR INHALER

Keep your inhaler clean and dry at all times. If the device needs cleaning, gently wipe the mouthpiece with a dry cloth or tissue as needed. Do not wash the inhaler. Avoid contact with any liquids.

Store in a dry place. Avoid storing it in damp or hot conditions such as a bathroom or in your car.

Keep your inhaler out of the reach of young children.

HOW TO KNOW WHEN YOUR INHALER IS EMPTY

The inhaler has a dose indicator window on the base. It is a dose counter which displays the number of doses remaining. When the unit reads "01", this indicates the last remaining dose. After dose "01", the counter will read "00", and the cap will lock and no additional dose will be delivered.

WHAT TO DO WITH YOUR USED INHALER

[figure not shown]
Please return your used TWISTHALER® device to the study site

Appendix 3 How to Use an Accuhaler®/ Diskus®

Instructions for use

Follow the instructions below for using your Diskus inhalation device. **You will breathe in (inhale) the medicine from the Diskus.** Do not use the Diskus unless your healthcare provider has taught you, and you understand everything. If you have any questions, ask the doctor, nurse or pharmacist personnel at the study site.

Figure 1 Parts of the Diskus

Take the Diskus out of the medication pack given to you. The Diskus will be in the closed position. The **dose indicator** on the top of the Diskus tells you how many doses are left. The dose indicator number will decrease each time you use the Diskus. After you have used 55 doses from the Diskus, the numbers 5 to 0 will appear in **red** to warn you that there are only a few doses left (see Figure 2).

Figure 2 Dose Indicator for the Diskus

[figure not shown]

Taking a dose from the Diskus requires the following 3 steps: Open, Click, Inhale.

1. OPEN

Hold the Diskus in one hand and put the thumb of your other hand on the **thumbgrip**. Push your thumb away from you as far as it will go until the mouthpiece appears and snaps into position (see Figure 3).

[figure not shown]
Figure 3 Opening the Mouthpiece Cover

2. CLICK

Hold the Diskus in a level, flat position with the mouthpiece towards you. Slide the **lever** away from you as far as it will go until it **clicks** (see Figure 4). The Diskus is now ready to use.

Figure 4 Sliding the Lever Until It Clicks

Every time the **lever** is pushed back, a dose is ready to be inhaled. This is shown by a decrease in numbers on the dose counter. **To avoid releasing or wasting doses once the Diskus is ready:**

- Do not close the Diskus.
- Do not tilt the Diskus.
- Do not play with the lever.
- Do not move the lever more than once.

3. INHALE

[figure not shown]
Before inhaling your dose from the Diskus, breathe out (exhale) fully while holding the Diskus level and away from your mouth (see Figure 5). **Remember, never breathe out into the Diskus mouthpiece.**

Figure 5 Exhaling

Put the mouthpiece to your lips (see Figure 6). Breathe in quickly and deeply through the Diskus. Do not breathe in through your nose.

Figure 6 Inhaling

[figure not shown]

Remove the Diskus from your mouth. Hold your breath for about 10 seconds, or for as long as is comfortable. Breathe out slowly. The Diskus delivers your dose of medicine as a very fine powder. Most patients can taste or feel the powder. Do not use another dose from the Diskus if you do not feel or taste the medicine.

4. CLOSE

Close the Diskus when you are finished taking a dose so that the Diskus will be ready for you to take your next dose. Put your thumb on the thumbgrip and slide the thumbgrip back towards you as far as it will go (see Figure 7). The Diskus will click shut. The lever will automatically return to its original position. The Diskus is now ready for you to take your next scheduled dose, due in about 12 hours. (Repeat steps 1 to 4 at that time).

Figure 7 **Closing the Mouthpiece Cover**

Remember:

- Never breathe into the Diskus.
- Never take the Diskus apart.
- Always ready and use the Diskus in a level, flat position.
- Do not use the Diskus with a spacer device.
- Never wash the mouthpiece or any part of the Diskus. **Keep it dry.**
- Always keep the Diskus in a dry place.
- Never take an extra dose, even if you did not taste or feel the medicine.

Appendix 4: Spirometry Guidance

Equipment

Spirometers must meet the specifications and performance criteria recommended in the American Thoracic Society (ATS)/European Respiratory Society (ERS) Standardization of Spirometry¹. Spirometers must have the capacity to print FVC tracings. All spirometry values should be reported at BTPS by the method established by the manufacturer.

Calibration

The spirometer should be calibrated every morning before any spirometric measurements for the study are performed. Calibration reports should be printed and stored as source data at the site.

Preparing the test subject

On study days when spirometry will be performed, patients should refrain from the following:

- Coffee, tea, chocolate, cola and other caffeine-containing beverages and foods and ice-cold beverages for 4 hours prior to spirometry
- Alcohol for 4 hours prior to spirometry
- Strenuous activity for 12 hours prior to spirometry
- Smoking within at least 1 hour of testing
- Exposure to environmental smoke, dust or areas with strong odors

Every effort should be made to assure consistent testing conditions throughout the study. A seated position with nose clips is recommended to reduce risks related to dizziness or syncope. When possible, spirometry should be conducted by the same technician using the same spirometer. To minimize the effects of diurnal variation on lung function, spirometry visits should start at approximately the same time of day at each visit.

Performing Spirometry

The subject's age, height and gender will be entered into the spirometer. It is important that the height is measured accurately at the study site. Spirometry, an effort-dependent test, requires careful instruction and cooperation of the subject. The technician should ensure a good seal around the mouthpiece, and confirm that the subject's posture is correct. The subject should be instructed to perform a maximal inspiration, followed by maximum forced expiration until no more air can be exhaled or for at least 6 seconds. Expiration must be rapid with exertion of maximal effort. The results of spirometry should meet the ATS/ERS criteria for acceptability and repeatability. Acceptability criteria should be applied before repeatability is determined.

Number of trials

A minimum of 3 acceptable forced vital capacity (FVC) maneuvers should be performed. If a subject is unable to perform a single acceptable maneuver after 8 attempts, testing may be discontinued.

Acceptability

An acceptable maneuver has the following characteristics:

- No hesitation or false start;

- A rapid start;
- No cough, especially during the first second of the maneuver;
- No glottic closure or obstruction by tongue or dentures
- No early termination of exhalation (minimum exhalation time of 6 seconds is recommended, and no volume change for at least 1 second) or the subject cannot continue to exhale further. Overall acceptability will be determined by expert over-read by spirometry vendor
-

Repeatability

The 2 largest FEV₁ values from 3 acceptable maneuvers should not vary by more than 0.150 L.

Recording of data

The highest FEV₁ and FVC from any of the acceptable curves are recorded. (The highest FEV₁ and FVC may not necessarily result from the same acceptable curve).

Predicted normal

This study will utilize the spirometric predication equation standards for the European Community for Coal and Steel², Nhanes³, ERS Global Lung Function Initiative (GLI)² or Japanese Respiratory Society³.

Reversibility

All reversibility evaluations should follow the recommendations of the ATS/ERS Task force: Standardization of Lung Function Testing

Administer 400 µg of salbutamol/albuterol following the completion of the baseline assessment. A second spirometry assessment is then performed within 15 to 30 minutes after administration of the salbutamol/albuterol.

Reversibility is calculated as:

$$100 \times \frac{\text{FEV}_1 (\text{post } \beta_2\text{-agonists}) - \text{FEV}_1 (\text{baseline})}{\text{FEV}_1 (\text{baseline})}$$

Subjects will be considered reversible if an increase of at least 12% (and 200 mL) is demonstrated after administration of the bronchodilator.

Predicted normal values will be calculated according to ECSC

For height measured in meters

Males: FEV₁ predicted (L)=4.30x(height(meters))-0.029xage(years)-2.49

Females: FEV₁ predicted (L)=3.95x(height(meters))-0.025xage(years)-2.60

References

¹ Miller MR et al, Standardization of Lung Function Testing. Eur Resp J 2005;26:153-161.

² Quanjer PH, et al. ERS Global Lung Function Initiative, Multi ethnic reference values for spirometry for the 3-95 year age range: the global lung function 2012 equations. Report of the Global Lung Function Initiative (GLI). ERS Task Force to establish improved Lung Function Reference Values.

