4.1 Inclusion criteria

Patients eligible for inclusion in this study must fulfill all of the following criteria:

1. Male and female adult and adolescent patients aged ≥ 12 years old (or ≥ 18 years old depending upon regulatory and/or IRB/IEC/REB approval and/or country participation) and ≤ 75 years

2. Written informed consent must be obtained before any study-related assessment is performed. Patients below the legal age of consent are required to have the Informed Consent Form signed by the patient's parent / guardian; adolescents are required to sign an assent form
3. Patients with a documented diagnosis of asthma for a period of at least 1 year prior to Visit 1 (Screening)
4. Patients who have used medium or high dose ICS (please refer to [Appendix 11](#) for guidance) or low dose of LABA/ICS combination for asthma for at least 3 months and at stable doses for at least 1 month prior to Visit 1
5. Patients must be symptomatic at screening despite treatment with mid or high stable doses of ICS and/or combinations of ICS (low dose) with long-acting beta adrenergic agent. Patients must have ACQ-7 score ≥ 1.5 at Visit 101 and at Visit 102 (prior to double-blind treatment) and qualify for treatment with medium or high dose LABA/ICS
 - In case that the spirometry is repeated due to a failure of meeting criteria 6, ACQ-7 should be repeated as well.
6. Pre-bronchodilator $FEV_1 \geq 50\%$ and $< 85\%$ of the predicted normal value for the patient according to ATS/ERS criteria after withholding bronchodilators (see [Table 5-2](#)) at both Visit 101 and 102
 - Withholding period of bronchodilators prior to spirometry:
 - SABA for ≥ 6 hours
 - FDC or free combinations of ICS*/LABA for ≥ 48 hours
 - SAMA for ≥ 8 hours
 - xanthines ≥ 7 days

Washout period of each drug should be kept as close as possible as above and should not be longer. If wash-out period is considered to be longer, please contact your Novartis Medical Monitor

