2.6.1.1.2 Key secondary variable ACQ-7 score

The ACQ-7 measures asthma symptom control and consists of 7 items: 5 on symptom assessment, 1 on rescue bronchodilator use, and 1 on airway calibre (FEV₁ % predicted). Patient recall is considered 1 week. All 7 questions of the ACQ-7 are equally weighted. Items 1-5 are scored along a 7-point response scale, where 0 = good controlled and 6 = poorly controlled. Item 6 is scored between 0 = no rescue medication and 6 = More than 16 puffs/inhalations most days. The 7th item will be scored by the investigator based on the FEV₁ % predicted from the masterscope at the site (i.e., Score = 0 means > 95% of predicted FEV₁, 1 = 90 – 95%, 2 = 80 – 89%, 3 = 70 – 79%, 4 = 60 – 69%, 5 = 50 – 59%, and Score = 6 means < 50% of predicted FEV₁). The total score is calculated as the mean of all questions. The mean will be calculated as the sum of scores divided by the number of questions that were answered, as long as there were at least 6 questions answered and the missing question is neither Question 1 ('On the average, during the past week, how often were you woken by your asthma during the night?') nor Question 7. In case of one missing response (not Question 1 or Question 7), that missing

response will be imputed as per the method given in the following paragraph and then the ACQ score will be calculated.

For a missing individual item while on-treatment, the interpolation method using either previous or subsequent completions of the questionnaire (ACQ User Guide, 2004) will be used. For instance,

Item	Visit 1	Visit 2
1	4	6
2	3	5
3	0	0
4	4	4
5	0	0
6	2	Missing
7	5	6

Total Visit 1 score for items answered on both visits is $4+3+0+4+0+5 = 16$ (A).

Total Visit 2 score for items answered on both visits is $6+5+0+4+0+6 = 21$ (B).

Item 6 score at Visit 1 = 2.

Item 6 score at Visit 2 = $B/A * 2 = 21/16*2 = 2.63$.

The ACQ score for Visit 1 is $(4+3+0+4+0+2+5)/7 = 2.57$

The ACQ score for Visit 2 is $(6+5+0+4+0+2.63+6)/7 = 3.38$

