For all spirometry measurements, we exclude the implausible values. Specifically, if a patient has implausible FEV₁ value (defined as > 7 L) at an assessment, all spirometry measurements related to that assessment will be excluded. The threshold of 7 L was chosen because according to ERS/ECCS 1993 regressions, the maximum normal predicted FEV₁ is 5.17 L, we set 7 L as the implausible cutoff to allow for some fluctuation around the maximum mean.

2.6.2.3 ACQ at Weeks 4, 12 and 52

ACQ-7 at Weeks 4, 12 and 52 will be analyzed using the same MMRM as specified for the key secondary endpoint ACQ-7 at Week 26. Change from baseline in the ACQ-7 will be also analyzed using the same MMRM model.

In addition, the proportion of patients who achieve an improvement of at least 0.5 in ACQ-7 (i.e., a decrease of ACQ-7 score of at least 0.5 from baseline) at Week 4, 12, 26, and 52 visits will be analyzed using a logistic regression model. First, missing continuous ACQ-7 values will be imputed using a MI method under MAR assumption. Then continuous ACQ values will be converted into binomial responses and generalized estimating equation (GEE) method will be used to analyze the imputed datasets and then the results from GEE method will be combined for the inference. The model will include the same terms as used for the analysis of ACQ-7 but no random effect for center nested within region. The estimated adjusted odds ratios will be displayed along with the associated 95% (two-sided) confidence intervals and p-values.

In addition to the contrast of QMF149 average vs. MF average, the individual treatment contrasts of QMF149 (150/160 µg) vs. MF 400 µg and QMF149 (150/320 µg) vs. MF 800 µg will be presented.

Additionally, the number (%) of patients will be summarized by visit with the following categories: Response (decrease from baseline of ≥ 0.5 units in ACQ-7), no change ($-0.5 <$ change from baseline in ACQ-7 < 0.5), worsening (increase from baseline of ≥ 0.5 units in ACQ-7). Net response is expressed as the number of patients with response – the number of patients with worsening.

All the analyses described above will be repeated for ACQ-5, including the responder analysis with the same threshold of 0.5..

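### Appendix 4 gives two conflicting rules for predicted FEV₁, and the only formulas it prints have no age limit although patients enrol from age 12

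*Protocol*

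**What the plan says.** Protocol Appendix 4 makes two statements about predicted normal values.

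- Under the paragraph on predicted normals: "This study will utilize the spirometric predication equation standards for the European Community for Coal and Steel", followed by NHANES, GLI or the Japanese Respiratory Society set. The four are joined by *or*, with no rule by age, region or site.
- After the reversibility text: "Predicted normal values will be calculated according to ECSC". Two formulas follow, for males "predicted (L)=4.30x(height(meters))-0.029xage(years)-2.49" and for females "predicted (L)=3.95x(height(meters))-0.025xage(years)-2.60". Neither has an age range or an age floor.

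The reference marks do not settle the matter. In the appendix, ECSC carries the mark of the GLI report and NHANES carries the mark of the Japanese reference. By their cited titles, the GLI report gives "Multi ethnic reference values for spirometry for the 3-95 year age range" and the Japanese reference covers adults.

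Inclusion criterion 1 (Protocol 4.1) admits "Male and female adult and adolescent patients aged ≥ 12 years old", and Protocol Section 4 expects adolescents to make up about 5% of 2000 patients.

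The SAP touches the equations twice. Section 2.6.1.1.2 says of the ACQ-7: "The 7th item will be scored by the investigator based on the FEV"₁ % predicted shown by the spirometer at the site. Section 2.6.2.2 supports its 7 L implausibility cut-off by noting that "according to ERS/ECCS 1993 regressions, the maximum normal predicted FEV"₁ is 5.17 L, without giving the height or age behind that figure.

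**The concern.** Percent predicted FEV₁ is a decision variable in this trial. It sets:

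- the entry limits of at least 50% and below 85% at Visits 101 and 102 (Protocol 4.1, criterion 6);
- item 7 of the ACQ-7, and so both the ACQ-7 entry threshold of 1.5 (criterion 5) and the key secondary endpoint;
- the per-protocol exclusion INCL06.A4 (SAP 16.1.9.2);
- the FEV₁ subgroups for efficacy (SAP 2.6.1.4) and for adverse events of special interest (SAP 2.7.2).

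Under the first statement, two sites could use different equations for the same patient and both comply, whether the patient is an adult or an adolescent. Under the second, formulas that subtract a fixed volume for every year of age are applied from age 12, which gives the youngest patients the highest predicted value at any given height. Adolescents are also a planned subgroup in their own right, so a doubtful classification of their lung function bears directly on how that subgroup is read.

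**Working it through.** **Inputs.** The two printed formulas (Protocol Appendix 4), with *h* height in metres and *a* age in years; the entry limits of 50% and 85%; the item 7 categories (Protocol Appendix 5: above 95% scores 0, 90–95% scores 1, 80–89% scores 2, 70–79% scores 3, and so on).

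- Male: 4.30*h* − 0.029*a* − 2.49
- Female: 3.95*h* − 0.025*a* − 2.60

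**The plan's own figure.** The SAP's 5.17 L can be reproduced only by assuming a height and an age. The male formula at 1.95 m and 25 years gives 8.385 − 0.725 − 2.49 = 5.17 exactly. It also gives 5.17 at 18 years and 1.903 m, and at 12 years and 1.862 m. If 1.95 m is the intended height, 5.17 L is not a maximum of the formula as printed: it gives 5.37 L at 18 and 5.55 L at 12. This hints at an unprinted lower age limit near 25 but does not prove one. The 7 L cut-off still lies above all these values.

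**Slope at fixed height.** From 12 to 17 years the prediction falls by 5 × 0.029 = 0.145 L (male) or 5 × 0.025 = 0.125 L (female), about 3.0% to 4.8% at heights of 1.40–1.80 m.

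**Illustration with an age floor (assumed; the documents state none).** Predicted FEV₁ in litres:

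| Sex, height | Age 12 | Age 18 | Age 25 | 12 vs 18 | 12 vs 25 |
|---|---|---|---|---|---|
| M, 1.40 m | 3.182 | 3.008 | 2.805 | +5.8% | +13.4% |
| M, 1.50 m | 3.612 | 3.438 | 3.235 | +5.1% | +11.7% |
| M, 1.80 m | 4.902 | 4.728 | 4.525 | +3.7% | +8.3% |
| F, 1.40 m | 2.630 | 2.480 | 2.305 | +6.0% | +14.1% |
| F, 1.50 m | 3.025 | 2.875 | 2.700 | +5.2% | +12.0% |
| F, 1.80 m | 4.210 | 4.060 | 3.885 | +3.7% | +8.4% |

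If age were held at 25, a 12-year-old's prediction would be too high by a factor of 1.083 to 1.141. Then:

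- Upper limit: 85 × 1.083 = 92 and 85 × 1.141 = 97. A patient at up to about 92–97% of the floored value reads below 85% and qualifies.
- Lower limit: 50 × 1.083 = 54 and 50 × 1.141 = 57. A patient between 50% and about 54–57% reads below 50% and is excluded.
- Item 7: a floored reading of 90% (score 1) becomes 90/1.083 = 83% (score 2) or 90/1.141 = 79% (score 3). One step is 1/7 = 0.14 on that patient's ACQ-7, and two steps are 2/7 = 0.29.

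**Effect on the ACQ-7 contrast.** If every adolescent (5%) were one step off, an arm mean would move by 0.05 × 1/7 = 0.007, and by 0.014 for two steps, against a planned difference of 0.15.

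**The case against.** The strongest reply is that the printed formulas may never have been applied to adolescents. Run-in medication is released on the spirometry equipment's verdict (Protocol 3.1 and 4.1), item 7 is read from the vendor's equipment (Protocol 6.4.2.1), and neither document says which equation set that equipment uses. It could already be GLI. This stands: a reader might infer that the entry criterion and item 7 are wrong for adolescents, but the documents state no validity range for the printed formulas and give no adolescent reference value against which to call them wrong. It does not remove the contradiction, which leaves the equation undefined at every age.

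A second tempting inference is that adolescents with normal lung function would qualify as obstructed. For a value of 100% to read below 85%, the prediction would have to be more than 100/85 = 1.176 times too high. Holding age at 25 gives at most 1.141, so 100% reads 88–92% and stays outside the limit. A larger overstatement, such as 20–50%, has no source in the documents.

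The fall with age also applies only at fixed height. A boy growing from 1.50 m at 12 to 1.70 m at 17 goes from 3.612 L to 4.327 L.

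Some protection is already in place. Entry also needs reversibility or historical evidence of it or of bronchoprovocation, judged without predicted values. Randomisation is stratified by age group, the model adjusts for age group and baseline ACQ-7, and the ACQ analyses are repeated for ACQ-5, which omits item 7. These protect the treatment contrast. They do not define who is eligible or which FEV₁ subgroup a patient falls in.

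**Conclusion.** The point holds as a conflicting rule behind a decision threshold. Appendix 4 permits four equation sets with no selection rule, then prescribes one, and prints it without an age limit in a trial that enrols from 12. Nothing in the documents supports the printed formulas at ages 12–17.

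The size of any error is unknown. The 8–14% figure is an illustration that assumes age held at 25, age 12, and heights of 1.40–1.80 m; holding age at 18 instead gives 3.7–6.0%. Those affected are about 0.05 × 2000 = 100 adolescents, about 20 per arm, through eligibility, item 7, the per-protocol exclusion and subgroup results. The missing selection rule also weakens comparability between sites for adults.

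A reader might go further and conclude that the trial's main results are biased. The documents do not support that: the primary endpoint is trough FEV₁ in litres and does not use % predicted, and a shift of about 0.007 per step in an ACQ-7 arm mean would largely cancel between arms.

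**What to change.** 1. Merge the two statements in Appendix 4 into one rule by age and region, and confirm that it matches what the vendor's equipment applies.
2. Do not apply the uncapped printed formulas to ages 12–17. Use the GLI set for them, which is already listed and is cited as covering 3–95 years.
3. Correct the reference marks, so that each equation set points to its own source.
4. For patients already enrolled, re-derive % predicted from recorded age, sex and height, and race where the equation needs it. Use the re-derived value for the FEV₁ subgroups and for a sensitivity version of the ACQ-7 with item 7 rescored.

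The analysis side costs one derived variable and one sensitivity run. The Appendix 4 change is an amendment that needs ethics committee approval (Protocol 11.1), and the equipment setting may have to change with it. Some adolescents would be classified differently from how they were at entry. Adolescent height is measured only at Visits 101, 207 and 214 or on early treatment discontinuation (Protocol 6.5.3), so rescoring item 7 at Visits 202 and 204 means carrying height forward from Visit 101, and the SAP should say so.
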